1.5.2.2. Maximum BCD-089 dose in the study

[REDACTED]

Translated from Russian to English, dated 06-Jul-2020

[REDACTED]

1.5.3. Rationale for the route of administration and dosing frequency

[REDACTED]

Translated from Russian to English, dated 06-Jul-2020

1.6. Clinical study compliance with standard regulatory requirements

This clinical study will be conducted in compliance with this Protocol, which is fully compliant with the legislation of the Russian Federation, National Standard of the Russian Federation, GOST R 52379-2005 “Good Clinical Practice”, as well as GCP standard.

1.7. Study population

Male healthy volunteers aged 18 to 45 years, inclusive who are eligible to participate in the study according to the Protocol eligibility criteria.

2. STUDY GOALS AND OBJECTIVES

2.1. Study aims

To evaluate tolerability, safety, and major pharmacokinetic and pharmacodynamic parameters of BCD-089 following single subcutaneous administration in increasing doses to healthy volunteers.

2.2. Study Objectives

1. To determine the safe dose range of BCD-089, which will subsequently be used in the phase II clinical study;
2. To determine the proportion of study participants in whom a single subcutaneous administration of BCD-089 was accompanied by the development of adverse events, including the proportion of volunteers with neutropenia of varying severity;

Translated from Russian to English, dated 06-Jul-2020

3. To determine the main pharmacokinetic parameters (AUC_{0-1680} , $AUC_{0-\infty}$, C_{max} , T_{max} , $T_{1/2}$, K_{el} and CL) of BCD-089 after a single subcutaneous injection in increasing doses to healthy volunteers;
4. To determine the main pharmacodynamic parameters (C_{max} , T_{max} , C_{min} , T_{min} , AUC_{0-1680}) for C-reactive protein, IL-6 and soluble receptor IL-6;
5. To determine the proportion of volunteers, in whom binding and/or neutralizing antibodies to BCD-089 were determined following its single administration.

3. HYPOTHESES TESTED

The study is based on the hypothesis that the maximum tolerated dose of BCD-089 with a single-dose subcutaneous injection to healthy volunteers is 2.9 mg/kg of body weight.

4. STUDY DESIGN

4.1 Primary and secondary parameters that will be assessed in the study

4.1.1. Pharmacokinetic endpoints

- AUC_{0-1680} (area under the concentration-time curve from the administration of the drug to 1680 h (71 days after administration) and $AUC_{0-\infty}$ (to infinity),
- C_{max} (maximum serum concentration of anti-IL-6 receptor antibody),
- T_{max} (time to maximum concentration);
- $T_{1/2}$ (half-life),
- K_{el} (elimination rate constant),
- CL (total clearance).

4.1.2. Pharmacodynamic endpoints

1. **C-reactive protein concentration determination:**

Translated from Russian to English, dated 06-Jul-2020

Primary:

- AUC_{0-1680} (area under the concentration-time curve from the administration of the drug to 1680 h (71 days after administration) and $AUC_{0-\infty}$ (to infinity).

Secondary:

- C_{min} (minimum detectable concentration in blood serum),
- T_{min} (time to minimum serum concentration).

2. **Determination of IL-6 concentration, soluble IL-6 receptor concentration:**

Primary:

- AUC_{0-1680} (area under the concentration-time curve from the administration of the drug to 1680 h (71 days after administration) and $AUC_{0-\infty}$ (to infinity).

Secondary:

- C_{max} (maximum concentration in serum),
- T_{max} (time to maximum serum concentration).

Additionally, the percentage of occupancy of membrane IL-6 receptors with BCD-089 2 hours after drug administration, 168, 336 and 504 hours after single injection will be determined in the study (however, it is not specified in the mandatory analyzed endpoints as it is a pilot study).

4.1.3. Subcutaneous injection-associated pain assessment endpoint

- The mean pain score during the injection on the visual analogue scale.

Translated from Russian to English, dated 06-Jul-2020

4.1.4. Safety endpoints:

- Proportion of subjects who developed SAEs in each cohort.
- Proportion of subjects who developed AEs in each cohort.
- Proportion of subjects who developed local reactions in each cohort.
- Proportion of subjects who developed grade 3-4 AEs in each cohort.
- Proportion of subjects who developed any grade neutropenia in each cohort.
- Proportion of subjects who discontinued the study due to AEs and SAEs in each cohort.

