The inclusion of volunteers in the study is sequential. The first to participate in the study is one volunteer, representing the cohort “01”, who was administered a single subcutaneous injection of BCD-089 at a dose calculated with an additional safety factor relative to the safe starting dose - 0.06 mg/kg. In the absence of grade 3-4 adverse events related to the test product, developing within the first 7 days after the injection, three volunteers are included in cohort 02. Further, the volunteer inclusion algorithm corresponds to the following general principle:

In the absence of any grade 3-4 AEs (DLT) associated with the test product within 7 days after the injection, the next cohort of three volunteers with dose escalation is included in the study - cohort 02 (cohort 03, cohort 04, etc.).

If grade 3-4 AEs (DLT) associated with the test product are recorded in only one volunteer in a cohort of three volunteers, three more healthy volunteers are additionally included in this cohort.

With the development of grade 3-4 AEs (DLT) associated with the test product in two of six volunteers, the dose at which this event was recorded will be taken as the maximum tolerated dose, further dose escalation will be ceased.

Thus, dose limiting toxicity will be assessed close to the time of administration, during the first seven days after the injection. However, it is not the end of the volunteers follow-up -

Translated from Russian to English, dated 06-Jul-2020

monitoring of their condition, as well as blood sampling for the study of pharmacokinetics, pharmacodynamics, and safety, will be carried out up to 71 days from the moment of injection.

A 14-day screening examination and 13 subsequent visits are planned to be conducted during the study. The duration of the active phase of the study (from the moment of the drug injection to the final visit) is 71 days.

The volunteer will need to be in a hospital for the entire duration of the first visit procedures (during which the test drug will be administered), since at this visit multiple blood sampling for PK studies will be performed. The volunteer will be able to leave the study site 24 hours after the administration of the test drug, provided he/she feels well and all prescribed blood sampling is completed. Starting from the "Day 3" visit, the volunteer must come to the study site approximately 1 hour before the PK blood sampling.

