4.6. Description of sequence and duration of all study periods

4.6.1 Schedule of study visits and procedures

The schedule of visits and their conduct are similar for the volunteers in all cohorts. A 14-day screening examination and 13 subsequent visits are planned to be conducted during the study. The first day of the study is the day of the first administered of BCD-089. The subsequent visits are calculated relative to the first BCD-089 administration. The frequency and timing of the study procedures are shown in Table 7.

Table 7. Listing and frequency of investigations and clinical examinations.

Study type	Control parameters	Frequency

[REDACTED]
 
[REDACTED]
 
[REDACTED]
	
[REDACTED]
 
[REDACTED]
 
 • [REDACTED] 	
[REDACTED]

[REDACTED]
	
 • [REDACTED] 	
[REDACTED]
 
[REDACTED]
 
[REDACTED]
 
[REDACTED]
 
[REDACTED]
 
[REDACTED]
 
[REDACTED]
 
[REDACTED]
 
[REDACTED]

[REDACTED]
 
[REDACTED]
	
 • [REDACTED] 	
[REDACTED]

[REDACTED]
 
[REDACTED]
	
 • [REDACTED] 	
[REDACTED]
 
[REDACTED]

Translated from Russian to English, dated 06-Jul-2020

Study type	Control parameters	Frequency

[REDACTED]
	
[REDACTED]
 
 [REDACTED] 	
[REDACTED]

[REDACTED]
	
 [REDACTED] 	
[REDACTED]

[REDACTED]
	
 [REDACTED] 	
[REDACTED]

[REDACTED]
	
 [REDACTED] 	
[REDACTED]

[REDACTED]
	
[REDACTED]
 
 [REDACTED] 	
[REDACTED]

[REDACTED]
	
 [REDACTED] 	
[REDACTED]

Translated from Russian to English, dated 06-Jul-2020

Table 9. Study flowchart.

Visit number	screening	1	2	3	4	5	6	7	8	9	10	11	12	13
Visit		Day 1	Day 2	Day 3	Day 4	Day 5	Day 6	Day 8	Day 11	Day 15	Day 22	Day 29	Day 50	Day 71
Day from the first injection	-14	0	1	2	3	4	5	7	10	14	21	28	49	70
Signing the Informed Consent Form	+													
Clinical and demographic data collection	+													
Assessment of vital signs	+	+ ²						+		+	+	+	+	+
Height measurement	+													
Body weight measurement	+	+												
Physical examination	+	+						+		+	+	+	+	+
Chest photofluorography	+													

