Pain assessment using VAS		+	+											
Complete blood count	+							+		+		+		+
	■	■	■	■	■	■	■	■	■	■	■	■	■	■
	■	■	■	■	■	■	■	■	■	■	■	■	■	■

² On day 1, the assessment of vital signs is performed prior to administration of the drug and 1 hour after it.

Translated from Russian to English, dated 06-Jul-2020

Visit number	screening	1	2	3	4	5	6	7	8	9	10	11	12	13
Visit		Day 1	Day 2	Day 3	Day 4	Day 5	Day 6	Day 8	Day 11	Day 15	Day 22	Day 29	Day 50	Day 71
Day from the first injection	-14	0	1	2	3	4	5	7	10	14	21	28	49	70
	■	■	■	■	■	■	■	■	■	■	■	■	■	■
	■	■	■	■	■	■	■	■	■	■	■	■	■	■
Blood chemistry test	+							+		+		+		+
Blood tests for infection markers	+													
Urinalysis	+							+						+
Alcohol breath test	+													
Urine drug test (psychotropic drugs, psychoactive medications)	+													
ECG	+							+						+
Study drug injection		+												
Concomitant therapy data collection	+	+	+	+	+	+	+	+	+	+	+	+	+	+
Recording of injection site reactions		+ ³	+		+			+		+		+		+

³ On Day 1, an assessment of injection site reactions is performed prior to administration of the drug and 8 hour after it.

Translated from Russian to English, dated 06-Jul-2020

Visit number	screening	1	2	3	4	5	6	7	8	9	10	11	12	13
Visit		Day 1	Day 2	Day 3	Day 4	Day 5	Day 6	Day 8	Day 11	Day 15	Day 22	Day 29	Day 50	Day 71
Day from the first injection	-14	0	1	2	3	4	5	7	10	14	21	28	49	70
AE/SAE recording	+ ⁴	+	+	+	+	+	+	+	+	+	+	+	+	+

⁴ Only SAEs should be registered at the screening.

Translated from Russian to English, dated 06-Jul-2020

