4.6.3.4. Complete blood count, blood chemistry, and urinalysis

Standard complete blood count testing methods shall be used under fasting conditions (8 hours without food). Test material – venous blood, volume drawn – at least 2 mL. This test includes the measurement of the following hematologic parameters:

- Hemoglobin, g/L

Translated from Russian to English, dated 06-Jul-2020

- Red blood cells (cells $\times 10^{12}/L$)
- Platelets (cells $\times 10^9/L$)
- White blood cells (cells $\times 10^9/L$)
- Neutrophils (cells $\times 10^9/L$)
- Lymphocytes (cells $\times 10^9/L$)
- Erythrocyte sedimentation rate (mm/h)

Standard blood chemistry testing methods are used under fasting conditions (8 hours without food, including sweet or alcoholic beverages). Test material – venous blood, volume drawn – at least 4 mL. The test includes determination of the following parameters:

- Total protein (g/L)
- Glucose (mmol/L)
- ALT (U/L)
- AST (U/L)
- Total bilirubin, $\mu\text{mol}/L$
- Creatinine, $\mu\text{mol}/L$

Standard urinalysis shall be performed with assessment of physical, chemical properties and sediment microscopy.

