8.2 Definitions

8.2.1 Adverse Events

Adverse event (AE): Any untoward medical event occurring in a participant of a clinical study after the administration of a medicinal product, which can have no causal relationship with the administration of the drug.

[figure not shown]
An AE is any untoward and unintended sign (including an abnormal laboratory finding), symptom, or disease, the time of occurrence of which does not exclude a causal relationship with the use of the drug, regardless of whether it is related or not, from the start of the study drug administration until day 28 inclusive after withdrawal of the volunteer from the clinical study.

As part of this study, the Investigator had to register all AEs, starting from grade 1 according to the classification, regardless of their clinical significance.

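### Neutropenia is a named endpoint and can be a DLT, yet the 7-day window holds one scheduled blood count, at 168 h, and there is no count on the dosing day

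*Combined protocol and SAP*

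**What the plan says.** Section 4.1.4 lists "Proportion of subjects who developed any grade neutropenia in each cohort" among the safety endpoints, and Section 8 repeats it. Objective 2 in Section 2.2 asks for the proportion with adverse events, "including the proportion of volunteers with neutropenia of varying severity".

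Neutropenia can also bear on escalation. Section 8.2.1 states: "An AE is any untoward and unintended sign (including an abnormal laboratory finding), symptom, or disease". Section 4.2 opens the next dose level "In the absence of any grade 3-4 AEs (DLT) associated with the test product within 7 days after the injection", and adds that "dose limiting toxicity will be assessed close to the time of administration, during the first seven days after the injection".

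Neutrophils are measured as part of the blood count (Section 4.6.3.4). In Table 9 (Section 4.6.1) the row "Complete blood count" is marked at screening and at visits 7, 9, 11 and 13. The table's time scale, "Day from the first injection -14 0 1 2 3 4 5 7 10 14 21 28 49 70", places those visits 7, 14, 28 and 70 days after injection (Days 8, 15, 29 and 71). Visits 1 to 6 carry no mark. Section 4.6.3.15 adds a count at an unscheduled visit if an adverse event occurs.

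**The concern.** A fall in neutrophils is usually silent and is found by testing. The plan makes neutropenia an endpoint and lets it act as a DLT, but tests for it once in the DLT window, on the last day. A silent grade 3-4 fall that recovers before 168 h would not enter the count that decides escalation in a first-in-human study.

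The baseline has a separate weakness. The only pre-dose count may be 14 days old at dosing, so up to 14 + 7 = 21 days can separate it from the first post-dose count. A fall that arose before the injection and was still present on Day 8 would be recorded as post-dose neutropenia.

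**Working it through.** **Inputs.** Count days are 7, 14, 28 and 70 (Table 9). The DLT window is days 0-7 (Section 4.2). Blood is already drawn for pharmacokinetics at 0, 2, 8, 12, 24, 48, 72, 96, 120, 168, 240, 336, 504, 672, 1176 and 1680 h (Section 9.1.1), so 48 h is Day 3, 96 h is Day 5, 504 h is Day 22 and 1176 h is Day 50.

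**The plan's own figure.** 1 sentinel + 6 cohorts x (3 + 3) = 37, which matches the stated maximum. Without expansions, and with every cohort opened, the total is 1 + 6 x 3 = 19.

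**Reading the schedule.** The same column mapping applied to the vital-signs row gives a Day 1 mark, which the table's footnote confirms. The gaps from dosing through successive counts are 168, 168, 336 and 1008 h.

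**Detection in the first week.** Assume onset uniform over days 0-7 and an episode of D days. It is detected if a count day lies between onset and onset + D. With one count at day 7 the probability is D/7, up to a maximum of 1. With counts at days 2, 4 and 7:
- D = 2 covers onsets 0-2, 2-4 and 5-7, so 6/7.
- D = 3 covers 0-2, 1-4 and 4-7, so 7/7.

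| Duration (days) | 168 h only | 48, 96 and 168 h |
|---|---|---|
| 2 | 29% | 86% |
| 3 | 43% | 100% |
| 4 | 57% | 100% |
| 5 | 71% | 100% |
| 6 | 86% | 100% |
| 7 or more | 100% | 100% |

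**What this could do to escalation (deliberately extreme case).** Take a true DLT rate of p = 0.30, all of it silent neutropenia, and let escalation follow 0 of 3, or 1 of 3 and then 0 of 3. The escalation probability is (1-p)^3 + 3p(1-p)^5 = 0.343 + 0.151 = 0.49. With only the 168 h count, p is replaced by 0.30 x D/7, which gives 0.93, 0.86 and 0.77 for episodes of 2, 3 and 4 days. With 48 h and 96 h added, 2-day episodes give p = 0.30 x 6/7 = 0.257 and a probability of 0.58; 3- and 4-day episodes give 0.49.

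**Detection over the whole follow-up.** Assume onset uniform over 70 days. The entries are covered days divided by 70.

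| Count days | 4-day episode | 7-day episode | 14-day episode |
|---|---|---|---|
| 7, 14, 28, 70 (now) | 16/70 = 23% | 28/70 = 40% | 42/70 = 60% |
| now + 2, 4 | 19/70 = 27% | 28/70 = 40% | 42/70 = 60% |
| now + 2, 4, 21, 49 | 27/70 = 39% | 42/70 = 60% | 56/70 = 80% |

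The Day 1 pre-dose count serves as baseline and detects no post-dose episode. The early counts matter for the DLT rule. For the 70-day endpoint nearly all the gain comes from Days 22 and 50.

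**The case against.** The strongest reply is that very short episodes may not be what this drug causes. Receptor occupancy is measured out to 504 h and sampling runs to 1680 h, which suggests effects lasting weeks. Any fall that starts in week 1 and lasts 7 days or more is seen. This stands: the loss for the DLT rule is confined to shorter falls, and uniform onset is only an assumption. Against it, Section 1.1 lists neutrophils among the cells that carry the receptor, and occupancy is measured from 2 h, so an early effect cannot be dismissed. Table 9 also gives injection-site reactions a pre-dose check and early post-dose checks.

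Volunteers attend on Days 1 to 6 with adverse events recorded each time, and a symptomatic event can lead to a count at an unscheduled visit (Section 4.6.3.15). That also stands, but it does not reach silent falls.

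Three stronger readings are tempting, and the documents do not support them:
- A reader might infer that the endpoint and the DLT count are both biased toward safety. Missed episodes lower the neutropenia proportion, but a fall before dosing raises it, so the net sign is not established. Such a fall could even add a DLT if it were grade 3-4 and judged related.
- A reader might take neutropenia to be the only toxicity with its own endpoint. Section 4.1.4 also names local reactions.
- A reader might say that severity is lost because the endpoint pools all grades. Section 9.2 (statistical analysis methods) already lists adverse events by severity grade, and Section 8.4.1 records them from grade 1, so this is minor.

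The frequencies in Table 7, the visit descriptions in Section 4.6.2 and some rows of Table 9 are blacked out and could not be checked. The blood-count row is fully legible.

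**Conclusion.** The point holds as a weakness of sampling frequency and baseline; no passages contradict each other. One scheduled count falls in the 7-day DLT window, at its end, and none falls on Day 1. Under uniform onset over days 0-7, detection of 2- to 6-day episodes runs from 29% to 86%, and nothing is lost from 7 days upward. The escalation figures show what is possible under an assumed 30% rate made up wholly of silent neutropenia; they are not a forecast. For the 70-day endpoint the larger gaps come after Day 15, and early counts alone barely help (23% to 27% for 4-day episodes, no change for 7 or 14 days). The change is worth making because it is cheap and uses draws that already take place.

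**What to change.** 1. Add a blood-count tube (at least 2 mL, Section 4.6.3.4) to the Day 1 pre-dose, 48 h (Day 3) and 96 h (Day 5) draws.
2. For the 70-day endpoint, add the same tube at the Day 22 and Day 50 draws.
3. Count as treatment-emergent any post-dose neutropenia whose CTCAE grade is worse than the Day 1 grade, and report the worst grade per volunteer by cohort.

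**Cost.** Five extra counts per volunteer: 5 x 19 = 95 in total with no expansions, or 5 x 37 = 185 at the maximum size. Blood is about 2 mL per count, or 5 x 2 = 10 mL per volunteer. No extra visit or venepuncture is needed. Section 4.6.3.4 requires an 8-hour fast for a blood count, and Section 4.2 sets no other dietary rule, so the fast must be written in for the added days. The blood volumes in Tables 4 to 6 are blacked out, so the total burden could not be checked. The reported neutropenia proportion will probably rise because more episodes are seen.

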4.1.5. Immunogenicity endpoint

- The frequency of development of binding and/or neutralizing antibodies to BCD-089 on Day 71 from the moment of a single-dose subcutaneous injection.

4.2 Design

Clinical study No. BCD-089-1 is a classic open-label, single-center, non-randomized cohort clinical study of the pharmacokinetics, pharmacodynamics, tolerability and safety of a novel drug in healthy volunteers at increasing doses (phase 1, 3+3 design).

Before being included in the study, healthy volunteers have to sign a written informed consent after having read it, after which they will undergo a 14-day screening examination to confirm compliance with the eligibility criteria for the study. No additional requirements regarding a certain diet or restriction of physical activity, both during the screening period and throughout the study, are specified in this protocol.

Study No. BCD-089-1 includes seven cohorts:

1. Cohort 01 - 1 volunteer to whom a single subcutaneous injection of BCD-089 at a dose of 0.06 mg/kg will be administered.
2. Cohort 02 - a maximum of 6 volunteers to whom a single subcutaneous injection of BCD-089 at a dose of 0.3 mg/kg will be administered.
3. Cohort 03 - a maximum of 6 volunteers to whom a single subcutaneous injection of BCD-089 at a dose of 0.625 mg/kg will be administered.

Translated from Russian to English, dated 06-Jul-2020

4. Cohort 04 - a maximum of 6 volunteers to whom a single subcutaneous injection of BCD-089 at a dose of 1.0 mg/kg will be administered.
5. Cohort 05 - a maximum of 6 volunteers to whom a single subcutaneous injection of BCD-089 at a dose of 1.6 mg/kg will be administered.
6. Cohort 06 - a maximum of 6 volunteers to whom a single subcutaneous injection of BCD-089 at a dose of 2.2 mg/kg will be administered.
7. Cohort 07 - a maximum of 6 volunteers to whom a single subcutaneous injection of BCD-089 at a dose of 2.9 mg/kg will be administered.

***Note.** If a volunteer is administered 1 mL of the solution and, therefore, it is necessary to perform two injections to administer the calculated dose, it is preferable to administer the drug to the same anatomical region, provided that the site of the subsequent injection is no closer than 5 cm from the previous one. The duration of administering several injections should not exceed 10 minutes; calculation of time for PK sampling starts from the “last” drug injection.

The inclusion of volunteers in the study is sequential. The first to participate in the study is one volunteer, representing the cohort “01”, who was administered a single subcutaneous injection of BCD-089 at a dose calculated with an additional safety factor relative to the safe starting dose - 0.06 mg/kg. In the absence of grade 3-4 adverse events related to the test product, developing within the first 7 days after the injection, three volunteers are included in cohort 02. Further, the volunteer inclusion algorithm corresponds to the following general principle:

In the absence of any grade 3-4 AEs (DLT) associated with the test product within 7 days after the injection, the next cohort of three volunteers with dose escalation is included in the study - cohort 02 (cohort 03, cohort 04, etc.).

If grade 3-4 AEs (DLT) associated with the test product are recorded in only one volunteer in a cohort of three volunteers, three more healthy volunteers are additionally included in this cohort.

With the development of grade 3-4 AEs (DLT) associated with the test product in two of six volunteers, the dose at which this event was recorded will be taken as the maximum tolerated dose, further dose escalation will be ceased.

Thus, dose limiting toxicity will be assessed close to the time of administration, during the first seven days after the injection. However, it is not the end of the volunteers follow-up -

Translated from Russian to English, dated 06-Jul-2020

monitoring of their condition, as well as blood sampling for the study of pharmacokinetics, pharmacodynamics, and safety, will be carried out up to 71 days from the moment of injection.

A 14-day screening examination and 13 subsequent visits are planned to be conducted during the study. The duration of the active phase of the study (from the moment of the drug injection to the final visit) is 71 days.

The volunteer will need to be in a hospital for the entire duration of the first visit procedures (during which the test drug will be administered), since at this visit multiple blood sampling for PK studies will be performed. The volunteer will be able to leave the study site 24 hours after the administration of the test drug, provided he/she feels well and all prescribed blood sampling is completed. Starting from the "Day 3" visit, the volunteer must come to the study site approximately 1 hour before the PK blood sampling.

Due to the need for multiple blood sampling, the volunteer has to stay at the study site for the first day after the injection.

Safety and tolerability assessment

Safety and tolerability will be assessed by monitoring vital signs (blood pressure, heart rate, and body temperature), conducting periodic physical examinations, assessing the frequency and severity of local reactions, and evaluating the results of complete blood count and blood biochemistry tests, urinalysis, and electrocardiography. These parameters will be assessed over a period of 71 days after a single-dose administration of the test drug. Additionally, information about the tenderness of subcutaneous injection, evaluated by a volunteer using a 10-point visual analog scale, will be analyzed.

Pharmacokinetic assessment

Pharmacokinetic assessment will be carried out based on data on the BCD-089 concentration in the serum of healthy volunteers. Volunteers included in the study arrive at the study site on the morning of the drug administration day. A venous catheter is installed immediately before the first blood sampling (the time from the catheter placement to the first blood sampling from it should not exceed one hour). Since multiple blood sampling is carried out only during the first day after the test drug administration, the time of placement a venous catheter will be 24 hours, after which the blood is taken by venipuncture. Detailed description of blood sampling points is presented in Table 3 below.

Translated from Russian to English, dated 06-Jul-2020

Pharmacodynamics and immunogenicity assessment

Pharmacodynamics assessment will be carried out based on data on the concentrations of C-reactive protein, soluble IL-6 receptor, human IL-6 in the serum of healthy volunteers.

Table 4. Detailed description of blood sampling for CRP, sIL-6R, IL-6 testing

Visit	Sample labeling number	Blood sampling time	Acceptable window for blood sampling	Blood volume (for 3 types of analyzed substances)
[REDACTED]	[REDACTED]	[REDACTED]	[REDACTED]	[REDACTED]
[REDACTED]	[REDACTED]	[REDACTED]	[REDACTED]	[REDACTED]
[REDACTED]	[REDACTED]	[REDACTED]	[REDACTED]	[REDACTED]
[REDACTED]	[REDACTED]	[REDACTED]	[REDACTED]	[REDACTED]
[REDACTED]	[REDACTED]	[REDACTED]	[REDACTED]	[REDACTED]
[REDACTED]	[REDACTED]	[REDACTED]	[REDACTED]	[REDACTED]
[REDACTED]	[REDACTED]	[REDACTED]	[REDACTED]	[REDACTED]
[REDACTED]	[REDACTED]	[REDACTED]	[REDACTED]	[REDACTED]
[REDACTED]	[REDACTED]	[REDACTED]	[REDACTED]	[REDACTED]

Translated from Russian to English, dated 06-Jul-2020

Visit	Sample labeling number	Blood sampling time	Acceptable window for blood sampling	Blood volume (for 3 types of analyzed substances)
██████	████████████████████	██████	██████	██████
██████	████████████████████	██████	██████	██████
██████	████████████████████	██████	██████	██████
██████	████████████████████	██████	██████	██████
██████	████████████████████	██████	██████	██████
██████	████████████████████	██████	██████	██████
██████	████████████████████	██████	██████	██████
██████	████████████████████	██████	██████	██████
██████	████████████████████	██████	██████	██████

Translated from Russian to English, dated 06-Jul-2020

Visit	Sample labeling number	Blood sampling time	Acceptable window for blood sampling	Blood volume (for 3 types of analyzed substances)
	[REDACTED]			

Translated from Russian to English, dated 06-Jul-2020

Additionally, the percentage of occupancy of IL-6 membrane receptors with BCD-089 will be determined. Detailed description of blood sampling points is presented in Table 5 below.

Table 5. Detailed description of blood sampling for IL-6 receptor occupancy assay

Visit	Sample labeling number	Blood sampling time	Acceptable window for blood sampling	Blood volume
██████	██████	██████	██████	██████
██████	██████	██████	██████	██████
██████	██████	██████	██████	██████
██████	██████	██████	██████	██████
██████	██████	██████	██████	██████

Table 6. Detailed description of blood sampling for immunogenicity assessment.

[figure not shown]
Visit	Sample labeling number	Blood sampling time	Acceptable window for blood sampling	Blood volume (for 3 aliquots)
██████	██████	██████	██████	██████
██████	██████	██████	██████	██████

Translated from Russian to English, dated 06-Jul-2020

Reporting:

[figure not shown]
The study report will be prepared after receiving data on the results of follow-up of the last volunteer included in the study.

Figure 7. Dose escalation scheme (starting from the cohort “02”).

Translated from Russian to English, dated 06-Jul-2020

Figure 8. Study flowchart

Translated from Russian to English, dated 06-Jul-2020

